- 13.9e Patient who complete retreatment without PD will go to observation followed by event monitoring. Patients who complete retreatment having PD will go to event monitoring.
- 13.9f **Ineligible**
- A patient is deemed *ineligible* if after registration, it is determined that at the time of registration, the patient did not satisfy each and every eligibility criteria for study entry. The patient may continue treatment off-protocol at the discretion of the physician as long as there are no safety concerns, and the patient was properly registered. The patient will go directly to the event-monitoring phase of the study (or off study, if applicable).
- If the patient received treatment, all data up until the point of confirmation of ineligibility must be submitted. Event monitoring will be required per Section 4.4 of the protocol.
  - If the patient never received treatment, on-study material must be submitted and the patient will go off study.

13.9g Major violation

A patient is deemed a *major violation*, if protocol requirements regarding treatment in cycle 1 of the initial therapy are severely violated that evaluability for primary end point is questionable. All data up until the point of confirmation of a major violation must be submitted. The patient will go directly to the event-monitoring phase of the study. The patient may continue treatment off-protocol at the discretion of the physician as long as there are no safety concerns, and the patient was properly registered. Event monitoring will be required per Section 4.4 of the protocol.

13.9h Cancel

A patient is deemed a *cancel* if he/she is removed from the study for any reason before any study treatment is given. On-study material and the End of Active Treatment/Cancel Notification Form must be submitted. No further data submission is necessary.

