#### 16.241 Adverse Events / Toxicity Profile (Goal 2.1.11)

The primary endpoint of the phase I portion is the incidence of dose-limiting toxicity. A dose-limiting toxicity is defined in section 7.61. Toxicities will be assessed using the CTEP Active Version of the CTCAE. Non-hematologic toxicities will be evaluated via the ordinal CTC standard toxicity grading. Hematologic toxicity measures of thrombocytopenia, neutropenia, and leukopenia will be assessed using continuous variables as the outcome measures (primarily nadir) as well as categorization via CTC standard toxicity grading.

These data will be assessed in evaluating the tolerability of the regimen for future studies. All patients meeting the eligibility criteria who have signed a consent form and have begun treatment will be considered evaluable for dose-limiting toxicity. Incidence of DLT will be estimated by the number of patients with DLT divided by the total number of evaluable patients. No more than three patients will receive the first cycle of combination immunotherapy (Pembrolizumab and cryoablation and DC injections, i.e. Cycle 2 of the overall treatment plan) at any time during Phase I of the study.

For a comprehensive picture of toxicity profile, we will also summarize the incidence of other significant toxicities as defined in Section 8 or as a Grade 3 or higher adverse event otherwise not described in Section 8, that is possibly, probably, or definitely related to treatment. The number and severity of all adverse events (overall and by dose level) will be tabulated and summarized in this patient population. The Grade 3+ adverse events will also be described and summarized in a similar fashion. This will provide an indication of the level of tolerance for this treatment combination in this patient group. Frequency distributions, graphical techniques and other descriptive measures will form the basis of these analyses. Further longitudinal analysis techniques will be employed to explore the adverse event profile over time.

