### 16.322 Secondary Outcome Analyses:

These analyses will include all patients meeting the eligibility criteria who have signed a consent form and have begun treatment. Analyses will include all patients enrolled in the Phase II portion of the study and analysis of each cohort separately.

16.323 Complete response (Goal 2.2.21): The response rate will be calculated, as above, in each individual cohort as supplementary to the primary analysis.

16.324 Progression free survival, treatment free survival, and duration of response (Goal 2.2.22):

Survival time is defined as the time from registration to death due to any cause. The distribution of survival time will be estimated using the method of Kaplan-Meier (Kaplan E 1958). In addition, the overall survival rate at 2 years after registration will be reported.

Treatment free survival time is defined for all evaluable patients who have achieved a response as the time from registration to next treatment or death due to any cause. The distribution of treatment-free survival will be estimated using the method of Kaplan-Meier. In addition, the disease-free survival rate at 2 years after registration will be reported.

Duration of response is defined for all evaluable patients who have achieved a PR or CR as the date at which the patient's objective status is first noted to be a response to the earliest date progression is documented. The distribution of duration of complete response will be estimated using the method of Kaplan-Meier.

16.325 Adverse Events (Goal 2.2.23): All eligible patients that have initiated treatment will be considered evaluable for assessing adverse event rate(s). The maximum grade for each type of adverse event at each evaluation will be recorded for each patient, and frequency tables will be reviewed to determine patterns. Additionally, the relationship of the adverse event(s) to the study treatment will be taken into consideration. Longitudinal analysis techniques will be utilized to determine the effect

of time on treatment adverse events.

16.326 Quality of Life (Goal 2.2.24):

Quality of life as measured using the FACT-Lym will be utilized. The assessment will be scored according to the scoring algorithm. Changes from baseline will be calculated at each assessment time points. Mean change scores at each time point will be calculated to determine if quality of life is reduced over the course of treatment. Longitudinal techniques will be employed to describe changes over time.

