## 16.5 Data & Safety Monitoring:

16.51 Routine monitoring of accrual and adverse events will be completed by the study statistical team on a weekly basis to assess patient safety.

16.52 Formal monitoring of accrual, adverse event, and any endpoint problems that might be developing will be conducted by the Mayo Clinic Cancer Center (MCCC) Data Safety Monitoring Board (DSMB). The DSMB is responsible for reviewing accrual and safety data for this trial at least twice a year, based on

reports provided by the MCCC Statistical Office.

- 16.53 Adverse Event Stopping Rules (These rules apply to each arm independently): The stopping rules specified below are based on the knowledge available at study development. We note that the Adverse Event Stopping Rule may be adjusted in the event of either (1) the study re-opening to accrual or (2) at any time during the conduct of the trial and in consideration of newly acquired information regarding the adverse event profile of the treatment(s) under investigation. The study team may choose to suspend accrual because of unexpected adverse event profiles that have not crossed the specified rule below.

Accrual will be temporarily suspended to this study if at any time we observe events considered at least possibly related to study treatment (i.e. an adverse event with attribute specified as “possible”, “probable”, or “definite”) that satisfy either of the following:

- Phase I portion:
  - Every 3 patients in the phase I portion of the trial will be monitored according to the criteria in Section 7.0 and Section 16.23.
  - Death (other than death related to progressive disease) that occurs within 30 days of the DC cell infusion.
- Phase II portion:
  - If 4 or more patients in the first 12 treated patients experience a grade 4 or higher non-hematologic adverse event at least possibly related to treatment excluding infections.
  - If after the first 12 patients have been treated, 30% of all patients experience a grade 4 or higher non-hematologic adverse event at least possibly related to treatment excluding infections
  - Death (other than death related to progressive disease) that occurs within 30 days of the DC cell infusion.

We note that we will review grade 4 and 5 adverse events deemed “unrelated” or “unlikely to be related”, to verify their attribution and to monitor the emergence of a previously unrecognized treatment-related adverse event.

- 16.54 Results Reporting on [REDACTED]

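### Phase II adverse event rates and phase I DLT incidence leave out treated patients later found ineligible, and no all-treated safety set is defined

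*Combined protocol and SAP*

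**What the plan says.** **Phase II.** Section 16.322 opens the secondary analyses with a general condition: "These analyses will include all patients meeting the eligibility criteria who have signed a consent form and have begun treatment". Section 16.325 repeats it for safety: "All eligible patients that have initiated treatment will be considered evaluable for assessing adverse event rate(s").

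**Phase I.** Section 16.241 says "All patients meeting the eligibility criteria who have signed a consent form and have begun treatment will be considered evaluable for dose-limiting toxicity", and then "Incidence of DLT will be estimated by the number of patients with DLT divided by the total number of evaluable patients". For the wider toxicity profile it says "The number and severity of all adverse events (overall and by dose level) will be tabulated and summarized in this patient population", with no separate statement about eligibility.

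**Losing eligible status.** Section 13.9f defines an ineligible patient as one found, after registration, to have failed any entry criterion at the time of registration. It expressly covers patients who have been treated: "If the patient received treatment, all data up until the point of confirmation of ineligibility must be submitted". They then move to event monitoring.

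**Stopping rules.** Section 16.53 has no eligibility condition. The first phase II rule reads "If 4 or more patients in the first 12 treated patients experience a grade 4 or higher non-hematologic adverse event". The second applies a 30% threshold to all patients once 12 have been treated, and the rule on non-progression deaths likewise does not mention eligibility.

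Section 16 defines no safety set of all treated patients.

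**The concern.** A safety rate should describe everyone exposed to the regimen. Here membership of the denominator depends on a status that can be decided after exposure, and after the adverse event itself. A patient may receive pembrolizumab, cryoablation and DC, have a high-grade event, and then be found to have missed an entry criterion. That patient's event is not in the planned phase II rate, and the patient is not in its denominator.

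Safety is the primary goal of phase I (2.11) and a secondary goal of phase II (2.223). With about 30 patients, moving one, two or three in or out of the set can change a reported rate noticeably. The report would also give adverse event rates on one population while accrual was monitored on another. A reader could not match the two without a listing of the patients who make up the difference.

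**Working it through.** **The plan's own safety figure.** The only safety probability in Section 16 is in 16.22: a toxicity of 25% incidence is seen at least once in 6 patients with probability at least 82%. It reproduces: 1 − (1 − 0.25)^6 = 0.822. It does not depend on the choice of safety set. No stated number bears directly on this point, so the check is to compare the sections and then illustrate the size.

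**Populations side by side**

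| Section | Quantity | Who is counted |
|---|---|---|
| 16.241 | Phase I DLT incidence | Eligible, consented, treatment begun |
| 16.241 | Phase I tabulation of all adverse events | Not stated separately |
| 16.325 | Phase II adverse event rates | Eligible, treatment begun |
| 16.53 | Phase II stopping rules | First 12 treated, then all patients |

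Taken with 13.9f, a treated patient later found ineligible is out of the first and third rows and in the fourth. For the second row, exclusion is only an inference.

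**Inputs for the illustration**
- Eligible treated patients: 28 (assumed; the additional phase II number in 16.12).
- Treated but ineligible patients: 3 (assumed ceiling). Section 16.12 allows 3 extra phase II patients, giving 28 + 3 = 31. That allowance also covers cancellations, major violations and other reasons. A cancelled patient has had no study treatment (13.9h), and 16.325 does not remove major violators. The number of treated ineligible patients within the allowance is therefore somewhere from 0 to 3. The documents give no rate.
- Events among the eligible: 3 (chosen for illustration).

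**Formulas.** With x events among the eligible and k among the ineligible, the planned rate is x/28 and the all-treated rate is (x + k)/31.

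Planned: 3/28 = 10.7%.

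| k | All-treated rate | Difference from 10.7% |
|---|---|---|
| 0 | 3/31 = 9.7% | −1.0 points |
| 1 | 4/31 = 12.9% | +2.2 points |
| 2 | 5/31 = 16.1% | +5.4 points |
| 3 | 6/31 = 19.4% | +8.6 points |

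**Direction.** The planned rate is too low only when the ineligible patients have the higher event proportion, that is when k/3 exceeds x/28. For x = 3 this needs k of at least 1 (1/3 against 0.107). With k = 0 the planned rate is slightly too high. The text of the plan fixes neither case.

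**The case against.** The strongest reply is that these patients remain under safety oversight. Section 10 requires serious adverse events to be reported whatever the patient's eligibility, and 10.8 carries this to 90 days after treatment (30 days if new anticancer therapy starts). The weekly statistical review and the DSMB review, at least twice a year, have no eligibility filter. The 16.53 rules count treated or all patients, and 13.9f requires data up to confirmation of ineligibility. All of this stands. A reader might infer that these patients vanish from the safety results; the documents do not support that. They leave the planned rate estimates only. Case reporting and monitoring, however, do not put them back into the rates for goal 2.223.

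A reader might also infer that the rule biases the rates downward because ineligible patients are the more fragile ones. The documents do not show this. Ineligibility under 13.9f covers every criterion, including histology, prior regimens and lesion count, and eligibility is verified at registration (6.32). Downward bias is plausible if a serious event prompts a second look at the chart, but no section describes such a review.

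A third tempting inference is that a DLT in a treated ineligible patient would be ignored and the MTD declared on 0 of 3. Section 16.23 words its rules by patients treated at a dose level, and its only replacement rule concerns failure to complete the first cycle for reasons other than toxicity. Neither 16.23 nor 16.241 says how such a DLT counts, so this is one reading among others. Phase I closed on July 9, 2018, and 7.5 already fixes phase II at dose level 1.

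Finally, 16.322 also says that analyses will include everyone enrolled in phase II. This sits awkwardly beside the eligibility condition in the preceding sentence, and 16.325, the specific rule for adverse events, still says eligible.

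**Conclusion.** The point holds as a defect in the definition of the analysis set. Followed as written, 16.325 and 16.241 remove exposed patients from the phase II adverse event rates and the phase I DLT incidence through a status that can be decided after exposure, and the final rates do not share a population with the stopping rules. This does not depend on which way any bias runs.

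Its size is modest to moderate and cannot be known in advance. Under the illustration, a reported 10.7% corresponds to between 9.7% and 19.4% of treated patients. That range assumes 28 eligible patients, 3 events among them, and the ceiling of 3 treated ineligible patients; with fewer ineligible patients the range narrows, and with none the issue has no numerical effect. For phase I the consequence is now one of reporting only.

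**What to change.** - **16.325:** define the safety set as all patients who received any study treatment, regardless of eligibility, so that it matches 16.53. Bring the general sentences in 16.322 into line for safety.
- **16.241:** report DLTs for all treated patients beside the evaluable count, and say which set the all-event tabulation uses.
- **Response:** keep the eligible-and-treated set for ORR.
- **Optional:** give eligible-only adverse event rates as a sensitivity analysis.
- **Follow-up:** for treated ineligible patients, state the length of adverse event follow-up. Section 13.9f requires full data only up to confirmation of ineligibility, and the event-monitoring schedule in 4.4 has no adverse event assessment, so later non-serious events may be missing.

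The cost is low. The data needed are already submitted under 13.9f, and the sample size, the rule of 13 or more responses in 28 and the stated 81% power do not change. The downsides are that rates may look slightly less favourable and that a few patients will have shorter follow-up for non-serious events. Extending collection for them would be a change to the protocol and the data collection, beyond a change of SAP wording, and is not needed for the set definition.

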## 16.4 Analysis of other endpoint

### 16.41 Definitions and Analyses of Radiologic Endpoints

Measurements of index lesion(s) (non-cryoablated lesion) will be evaluated over time for each patient as a marker of systemic immune and treatment response to Pembrolizumab and localized treatment with cryoablation and DC. The index lesion(s) will be selected by the treating physician/investigator and are non-cryoablated node. The percent change from baseline in index lesion measurements will be assessed over time. Differences in values over time will be summarized descriptively and graphically. In addition, patients will be classified into one of the following categories based on the best response seen in the index lesion(s):

- Complete response: disappearance of the node
- Partial response:  $\geq 50\%$  of decrease in measured dimension
- Stable: between  $50\%$  decrease to  $\leq 25\%$  increase in dimension
- Progression:  $>25\%$  increase in measured dimension

While the evaluation of index lesion(s) may be part of the assessment of overall response, it is not the sole criteria for time to progression. The whole body CT or PET/CT will be used to assess overall clinical response and time to progression using the standard Cheson criteria, as detailed in Section 11.

### 16.42 Correlative Endpoints

Change in immunologic correlates before and after vaccination treatment will be evaluated and summarized both quantitatively and graphically. Each of the correlative endpoints will be summarized individually, but will also be evaluated in terms of their relationships to one another; i.e., we will use Spearman rank correlation coefficient to assess the correlations between baseline levels as well as between changes before and after treatment in these immunologic markers. In addition, these immunologic markers will be correlated with cancer and treatment-related outcomes (e.g. response, toxicities). Relationships will also be explored graphically using scatter plots. Given the limited sample size, these analyses will be considered exploratory.

## 16.5 Data & Safety Monitoring:

16.51 Routine monitoring of accrual and adverse events will be completed by the study statistical team on a weekly basis to assess patient safety.

16.52 Formal monitoring of accrual, adverse event, and any endpoint problems that might be developing will be conducted by the Mayo Clinic Cancer Center (MCCC) Data Safety Monitoring Board (DSMB). The DSMB is responsible for reviewing accrual and safety data for this trial at least twice a year, based on

reports provided by the MCCC Statistical Office.

- 16.53 Adverse Event Stopping Rules (These rules apply to each arm independently): The stopping rules specified below are based on the knowledge available at study development. We note that the Adverse Event Stopping Rule may be adjusted in the event of either (1) the study re-opening to accrual or (2) at any time during the conduct of the trial and in consideration of newly acquired information regarding the adverse event profile of the treatment(s) under investigation. The study team may choose to suspend accrual because of unexpected adverse event profiles that have not crossed the specified rule below.

Accrual will be temporarily suspended to this study if at any time we observe events considered at least possibly related to study treatment (i.e. an adverse event with attribute specified as “possible”, “probable”, or “definite”) that satisfy either of the following:

- Phase I portion:
  - Every 3 patients in the phase I portion of the trial will be monitored according to the criteria in Section 7.0 and Section 16.23.
  - Death (other than death related to progressive disease) that occurs within 30 days of the DC cell infusion.
- Phase II portion:
  - If 4 or more patients in the first 12 treated patients experience a grade 4 or higher non-hematologic adverse event at least possibly related to treatment excluding infections.
  - If after the first 12 patients have been treated, 30% of all patients experience a grade 4 or higher non-hematologic adverse event at least possibly related to treatment excluding infections
  - Death (other than death related to progressive disease) that occurs within 30 days of the DC cell infusion.

We note that we will review grade 4 and 5 adverse events deemed “unrelated” or “unlikely to be related”, to verify their attribution and to monitor the emergence of a previously unrecognized treatment-related adverse event.

- 16.54 Results Reporting on [REDACTED]

At study activation, this study will have been registered within the [REDACTED] website. The Primary and Secondary Endpoints (i.e., “Outcome Measures”) along with other required information for this study will be reported on [REDACTED]. For purposes of timing of the Results Reporting, the initial estimated completion date for the Primary Endpoint of this study is 4 years after the study opens to accrual. The definition of “Primary Endpoint Completion Date” (PECD) for this study is at the time the last patient registered has been observed for 12 months.

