#### 7.113 Pembrolizumab, monoclonal anti-PD1 antibody

Patients will receive pembrolizumab at 200 mg IV every 3 weeks for 18 cycles. If patient experienced adverse events requiring dosing delay (see Section 8), the new dosing interval (increased interval) can be defined as the new cycle length. Patients who achieved CR before Cycle 5 will complete treatments through cycle 6 and can then stop treatment at the discretion of the treating provider and investigators. Patients who achieved CR at or after cycle 5 could continue treatments for 2 more cycles and stop treatment at the discretion of the treating provider. The designed maximum length of treatment is 12 months (365 days). If the patient is continuing to benefit from treatment after 12 months, the patient may continue to receive treatment up to 24 months at investigator/sponsor discretion.

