## 8.2 Treatment schedule modifications for pembrolizumab

Adverse events (both non-serious and serious) associated with pembrolizumab exposure may represent an immunologic etiology. These adverse events may occur shortly after the first dose or several months after the last dose of treatment. Pembrolizumab must be withheld for drug-related toxicities and severe or life-threatening AEs per Table 8.21 below. See Section 9.0 for supportive care guidelines, including use of corticosteroids.

**Table 8.21** Dose Modification Guidelines for Drug-Related Adverse Events for Pembrolizumab

CTCAE System/Organ/Class (SOC)	Adverse Event	Hold Treatment for Grade	Timing for Restarting Treatment	Treatment Discontinuation
Gastrointestinal disorders	Diarrhea or Colitis	2-3	AE resolves to Grade 0-1	AE does not resolve within 12 weeks of last dose or inability to reduce corticosteroid to 10 mg or less of prednisone or equivalent per day within 12 weeks
		4	Permanently discontinue	Permanently discontinue
Investigations	AST, or ALT, or Blood bilirubin	2	AE resolves to Grade 0-1	AE does not resolve within 12 weeks of last dose.
		3-4	Permanently discontinue (see exception below) a	Permanently discontinue
Metabolism and nutrition disorders	Glucose intolerance (Type 1 diabetes mellitus [if new onset]) or Hyperglycemia	T1DM or 3-4	Hold pembrolizumab for new onset Type 1 diabetes mellitus or Grade 3-4 hyperglycemia associated with evidence of beta cell failure	Resume pembrolizumab when patients are clinically and metabolically stable.
Endocrine disorders	Endocrine disorders – Other, specify: Hypophysitis	2-4	AE resolves to Grade 0-1. Therapy with pembrolizumab can be continued while endocrine replacement therapy is instituted	AE does not resolve within 12 weeks of last dose or inability to reduce corticosteroid to 10 mg or less of prednisone or equivalent per day within 12 weeks

CTCAE System/Organ/Class (SOC)	Adverse Event	Hold Treatment for Grade	Timing for Restarting Treatment	Treatment Discontinuation
Endocrine disorders	Hyperthyroidism	3	AE resolves to Grade 0-1	AE does not resolve within 12 weeks of last dose or inability to reduce corticosteroid to 10 mg or less of prednisone or equivalent per day within 12 weeks
		4	Permanently discontinue	Permanently discontinue

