#### 10.52 Death

**Note: A death on study requires both routine and expedited reporting regardless of causality, unless as noted below. Attribution to treatment or other cause must be provided.**

Any death occurring within 30 days of the last dose, regardless of attribution to an agent/intervention under an IND/IDE requires expedited reporting within 24-hours.

Any death occurring greater than 30 days with an attribution of possible, probable, or definite to an agent/intervention under an IND/IDE requires expedited reporting within 24-hours.

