## 10.6 Required Routine Reporting

### 10.61 Baseline and Adverse Events Evaluations

Pretreatment symptoms/conditions to be graded at baseline and adverse events to be graded at each evaluation.

Grading is per CTCAE v4.0 **unless** alternate grading is indicated in the table below:

CTCAE System/Organ/Class (SOC)	Adverse event/Symptoms	Baseline	Each evaluation
Investigations	Platelet count decreased	X	X
	Neutrophil count decreased	X	X
Blood and lymphatic system disorders	Anemia	X	X
Gastrointestinal disorders	# of stools	X	
	Diarrhea		X
	Nausea	X	X
	Vomiting	X	X
Respiratory, thoracic and mediastinal disorders	Cough	X	X
	Dyspnea	X	X
	Pneumonitis	X	X
Skin and subcutaneous tissue disorders	Rash maculo-papular	X	X

10.62 Submit via appropriate MCCC Case Report Forms (i.e., paper or electronic, as applicable) the following AEs experienced by a patient and not specified in Section 10.6:

10.621 Grade 2 AEs deemed *possibly, probably, or definitely* related to the study treatment or procedure.

10.622 Grade 3 and 4 AEs regardless of attribution to the study treatment or procedure.

10.623 Grade 5 AEs (Deaths)

10.6231 Any death within 30 days of the patient's last study treatment or procedure regardless of attribution to the study treatment or procedure.

10.6232 Any death more than 30 days after the patient's last study treatment or procedure that is felt to be at least possibly treatment related must also be submitted as a Grade 5 AE, with a CTCAE type and attribution assigned.

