Blood and lymphatic system disorders: immune thrombocytopenic purpura, hemolytic anemia

Immune system disorders: sarcoidosis

Nervous system disorders: Guillain-Barre syndrome, myasthenic syndrome, exacerbation of myasthenia gravis

Gastrointestinal disorders: small intestinal perforation

Skin and subcutaneous tissue disorders: toxic epidermal necrolysis, Stevens-Johnson syndrome, erythema nodosum

The risk profile for pembrolizumab also includes two important potential risks: a) myasthenic syndrome, and b) an increased risk of severe complications (such as early severe graft versus host disease and veno-occlusive disease) of allogeneic transplant in patients with hematologic malignancies who have previously been treated with PD-1 inhibitors.

Patients with multiple myeloma who were treated with pembrolizumab in combination with either pomalidomide or lenalidomide and dexamethasone, had an increased number of serious side effects and deaths as compared to patients who received only dexamethasone and either pomalidomide or lenalidomide. The benefit-risk profile is unfavorable for the combination of pembrolizumab, pomalidomide, and dexamethasone in relapsed refractory multiple myeloma, and the combination of pembrolizumab, lenalidomide, and dexamethasone in newly diagnosed treatment-naive multiple myeloma.

Post marketing reports identified Vogt-Koyanagi-Harada syndrome and hemophagocytic lymphohistiocytosis.

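### The phase II single-death suspension rule in 16.53 is tied to DC, so 12 of 18 pembrolizumab doses fall after its window and some related deaths meet no mandatory trigger

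*Combined protocol and SAP*

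**What the plan says.** Section 16.53 requires a temporary halt to phase II accrual for events at least possibly related to treatment, in three cases. Two are rate rules, 4 or more of the first 12 treated patients and then 30% of all patients. Both count patients who "experience a grade 4 or higher non-hematologic adverse event at least possibly related to treatment excluding infections". The third acts on a single event: "Death (other than death related to progressive disease) that occurs within 30 days of the DC cell infusion".

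Beyond these triggers, 16.53 gives the team discretion: "The study team may choose to suspend accrual because of unexpected adverse event profiles that have not crossed the specified rule below". Section 16.51 provides weekly review by the statistical team, and 16.52 a safety board review at least twice a year.

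On exposure, 7.113 states: "Patients will receive pembrolizumab at 200 mg IV every 3 weeks for 18 cycles". Section 7.111 places the eight DC injections in Cycles 2 to 5, and 7.5 applies that schedule to phase II. Section 13.2 allows up to 18 further pembrolizumab cycles.

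On the timing of pembrolizumab toxicity, 8.2 says: "These adverse events may occur shortly after the first dose or several months after the last dose of treatment". Section 15.17 includes among the rare but important or life-threatening toxicities: "Blood and lymphatic system disorders: immune thrombocytopenic purpura, hemolytic anemia".

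**The concern.** The one trigger that responds to a single death follows the agent given for the shorter time. Inside its window, any related death not due to progression pauses accrual, including a fatal infection. Outside it, the same death is handled in one of two ways:

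- If it is neither hematologic nor infectious, it adds one patient to a rate rule.
- If it is hematologic or infectious, it adds to nothing, because both rate rules exclude those categories.

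Phase I did not exclude them. Section 7.16 made related grade 3 or higher infection, and grade 4 neutropenia or thrombocytopenia lasting 7 days or more, dose-limiting. In phase II the single-death bullet is the only mandatory trigger left for them, and it lapses 30 days after the last DC injection. Section 9.2 foresees opportunistic infection during prolonged steroid treatment of pneumonitis, so a related infection is not far-fetched.

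At stake is whether patients keep enrolling after a treatment-related death. In Cycle 1, or from about Cycle 7 onward, that depends on someone choosing to pause, although the protocol treats the same death as sufficient on its own a few weeks later or earlier.

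**Working it through.** **Inputs.** Cycle length is 21 days (7.111). Pembrolizumab is given on Day 1 of Cycles 1 to 18. DC is given on Days 2, 8 and 15 of Cycles 2 and 3, and on Day 2 of Cycles 4 and 5. The trigger runs 30 days from DC (16.53). Phase II accrual is a maximum of 31 patients (16.12) over about 22 months (16.13).

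**Schedule.** Study day = 21 × (cycle − 1) + day in cycle.

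- DC days: 23, 29, 36, 44, 50, 57, 65, 86. That is 8 doses, as 7.111 states.
- Pembrolizumab days: 1, 22, 43, …, 358. That is 18 doses, as 7.111 states.

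**Window.** The longest gap between DC doses is 21 days, so the 30-day periods join without a break. The window runs from day 23 to day 86 + 30 = 116, which is 116 − 23 + 1 = 94 days.

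| Pembrolizumab doses | Days | Number |
|---|---|---|
| Before the window | 1, 22 | 2 |
| Inside | 43, 64, 85, 106 | 4 |
| After | 127 to 358 | 12 |

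The count of 12 does not change if the end of the window shifts by up to 4 days either way. Other readings and scenarios:

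- 16.53 does not say which DC dose starts the clock. If it is the first, the window ends on day 53 and 15 of 18 doses follow it.
- If DC runs out early and the patient moves to Cycle 6, 11 or 12 of 15 to 17 doses follow it.
- With the optional year and no retreatment, 30 of 36 doses follow it.

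**Share of time covered.** Follow-up to 30 days after the last dose ends on day 358 + 30 = 388, and 94 / 388 = 24%. This is a share of calendar days, not of risk.

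Patients will also stop early. I assumed exponential time on treatment capped at day 358, with patients at risk until last dose + 30 and covered until last DC + 30. The last column counts only days before accrual closes, with uniform entry over 22 × 30.4 = 669 days.

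| Median time on treatment | Covered, all at-risk days | Covered, accrual still open |
|---|---|---|
| No early stopping | 24% | 31% |
| 12 months | 30% | 36% |
| 6 months | 36% | 41% |
| 3 months | 46% | 49% |
| 2 months | 51% | 54% |

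**Timing against accrual.** A patient passes day 116 before accrual ends if entered at least 117 days earlier: (669 − 117) / 669 = 83%, if still followed.

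**What one death adds outside the window.** A related death that is neither infectious nor hematologic is 1 of the 4 patients needed in the first 12. At 28 treated, 0.30 × 28 = 8.4, so it is 1 of 9. At 13 treated, 0.30 × 13 = 3.9, so it is 1 of 4. A related fatal infection or hematologic death adds 0 to either rule.

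**Enrolment between scheduled board reviews.** Reviews may be 6 months apart: 31 / 22 × 6 = 8.5, about 8 patients. Section 16.31 gives 22 to 25 patients from phase II instead, which gives 6.0 to 6.8. The stated 1 to 3 patients per month gives 6 to 18.

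**The case against.** The wording and the arithmetic are not in dispute. The case on the other side concerns weight.

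- **The complete gap is narrow.** It needs a death that is related, infectious or hematologic, outside the window, and before accrual closes. Section 15.17 puts immune thrombocytopenic purpura and hemolytic anemia each below 0.1%, so in 34 patients fewer than 34 × 0.001 = 0.034 cases of each are expected, and not all would be fatal. This stands and limits the urgency. It does not cover infection, nor the weaker handling of all other related deaths outside the window.
- **The 12 of 18 count overstates the practical gap.** Patients stop early, complete responders may stop sooner (7.113), retreatment reopens the window for those with stored DC (7.4), and the rule matters only during accrual. This is fair, and the last column above is the better measure. It still leaves 46% to 69% of at-risk days uncovered, and the optional year adds more uncovered time.
- **A related death would not go unnoticed.** Reports go to the sponsor, the drug supplier and, where criteria are met, the FDA and the IRB. Weekly review continues, and 16.53 lets the rule be adjusted at any time. All true. These make the death known, but none requires a pause, and the discretionary clause speaks of unexpected event profiles.
- **Tying the automatic pause to the newer component is defensible.** Pembrolizumab had already been given to 1,000 patients (1.36). But the trial tests the combination, and the protocol gives no reason for treating a related death on day 117 differently from one on day 116.
- **A trigger with no end date may catch late deaths rated only as possible, even after other therapy.** This is a real cost. A window of 30 days after the last dose of any agent would cover all 18 doses, to day 388, but would miss the late events that 8.2 anticipates.

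**Conclusion.** The concern holds. Section 16.53 has no mandatory phase II trigger for a related fatal infection or hematologic death outside the DC window, and only a diluted one for any other related death there. In the planned initial course, without delays or retreatment, 14 of 18 pembrolizumab doses fall outside the window, 12 of them after it. That count measures the window from the last DC dose, the reading most favourable to the plan.

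The covered share of at-risk time while accrual is open is 31% with no early stopping and 36% to 54% under the assumed early-stopping patterns. Those patterns and uniform entry are my assumptions, and time shares are not risk shares. The documents give no basis for estimating the rate of such deaths, which is probably low. The change is still worth making, because it is cheap and concerns patient safety. The textual finding is secure; its practical frequency is not known.

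**What to change.** Replace the phase II death bullet in 16.53 with a trigger for any death, other than one related to progressive disease, that is judged at least possibly related to any study agent or procedure, whenever it occurs after the first study treatment. This also removes the doubt about which DC dose starts the 30 days.

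Leave the exclusion of infections in the two rate rules alone, since removing it would mean recalibrating the 4 of 12 and 30% thresholds. The identical phase I bullet needs no change because phase I is closed to accrual.

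No new data collection is needed. Section 10.52 already requires 24-hour reporting of "Any death occurring greater than 30 days with an attribution of possible, probable, or definite to an agent/intervention under an IND/IDE". Section 10.6232 uses this wording for deaths beyond 30 days: "last study treatment or procedure that is felt to be at least possibly treatment related must also be submitted as a Grade 5 AE". Related deaths within 30 days of the last dose are captured in the same two sections. The cost is one bullet of amended wording and an occasional extra temporary pause, including for some deaths rated as possible that review then judges unrelated.
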